Our research group recently conducted a large-scale multicenter randomized controlled trial of electronic alerts for AKI throughout the Yale New Haven Health System from 2018 to 2020. The trial, which enrolled 6,030 patients with AKI, as defined by an increase in creatinine of 0.3mg/dL over 48 hours or 50% over 7 days, randomized patients between usual care and an intervention group whereby providers received a general AKI alert informing them to the presence of AKI and the patient's recent creatinine trends, and provided a link to an AKI-specific order set. Our study showed that, overall, alerting physicians to the presence of AKI did not demonstrate a difference in the rate of our primary outcome of progression of AKI, dialysis, or death, nor were there any differences in process measures accessed (i.e. provider actions) between the two groups, however, there was substantial heterogeneity among the study sites. Stratification of results by hospital revealed that signals of harm exist in the two non-teaching hospitals of our study, where a higher relative risk for our primary outcome was seen in the intervention group. This increased risk was shown to be driven by an increased number of deaths in the alert group, however, process measures still remained unchanged. The alert in this study was limited by the fact that it was purely informational. While an order set was provided, there were no associated patient-specific recommendations or guidance. Given the highly heterogeneous nature of AKI, a more personalized approach may be warranted. Further, this study enrolled all patients who developed AKI rather than a targeted subset of patients who may benefit, such as those AKI patients receiving potentially harmful kidney-toxic medications.

[figure not shown]
In the present proposal, we seek to expand upon our prior study to determine if the use of medication-targeted electronic alerts will modify provider behavior, particularly in regards to nephrotoxic medication use and cessation, in the care of hospitalized patients with AKI and/or reduce the rates of progression to AKI, dialysis, or mortality in hospitalized patients. Given the heterogeneous and surprising results of our prior study, it is of utmost importance that the efficacy of such interventions, even those that are seemingly benign, are rigorously evaluated in the setting of a randomized controlled trial.

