- Risk of increased signals of harm in the alert group. As discussed above, our recent AKI alert trial showed signals of harm of our general AKI alert, as shown by an increased relative risk of the primary outcome, in the two non-teaching hospitals of our study. Because of this, we will no longer be enrolling in the non-teaching hospitals for this study.

11. Minimizing Risks: Describe the manner in which the above-mentioned risks will be minimized.

- There is limited risk to the loss of confidentiality, as only de-identified data is being stored for analysis. All data in this study will be stored on a central server within the Program of Applied Translational Research. The server is only accessible from within the Yale intranet (or via VPN remotely) and additionally requires separate logon username and password.

Data abstracted from the medical record will be de-identified, with a linking file retained in a separate location that will allow for future linking of de-identified data to protected health information (PHI) for the purpose of potential future studies. Studies that require the use of PHI (for example, linking patient info to national outcomes databases) will require approval of both the manuscript and executive committees and a separate IRB approval. De-identified data will be stored on a secure server, accessed via "dumb" terminals, and all analyses will proceed on that server alone. De-identified data will be transmitted to outside investigators using secure, encrypted channels upon approval of the manuscript committee.

The study is not causing any novel data to be gathered about any patient; it only gathers data from already-existing electronic health records. No PHI are included in the data being analyzed or published. Study participants therefore face no greater dangers of loss of confidentiality than they already face as patients.

This data is not subject to any data sharing agreements at this time. As this will be a large and useful data set that may be utilized in future research protocols, we plan to maintain both the de-identified data set and the linking dataset for at least the duration of IRB approval, and will seek permission to maintain those files on a yearly basis from the IRB if the research protocol is renewed.

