A group sequential design with Hwang-Shih-DeCanli spending functions with gamma = -4 for the efficacy boundary and gamma = -2 for the futility boundary with two interim analyses will be utilized and a two-sided Cochran-Mantel-Haenszel (CMH) method will be used for the sample size calculation to account for the four hospitals. Our preliminary data suggests that 18.2% of patients would experience the primary outcome of progression of AKI, dialysis, or mortality. We determined that a relative 20% reduction to 14.6% would be clinically significant. A total sample size of 4600 patients (i.e., 2301 per group) achieves at least 90% power to detect this degree of change. The alpha significance level of the test was set at 0.05. We will increase this

number by 10% to account for potential contamination of the effect across study arms, leading to a final sample size of 5060 individuals with a breakdown as follows based on relative numbers of beds in each hospital:

Yale New Haven Hospital: 2447

St. Raphael's Campus: 1214

Bridgeport Hospital: 910

Greenwich Hospital: 489

We will compare the rates of the primary outcomes between the intervention arm and the control arm using the chi-square test with Cochran-Mantel-Haenszel correction for the 4 study strata based on the hospital.. We will also perform exploratory analyses examining patients within the three medication categories to assess whether discontinuation rates differ by medication and, importantly, what clinical impact is apparent from alerting for those particular agents. Finally, should alerting show a clinical benefit, we will perform a mediation analysis to determine what fraction of that benefit (if any) can be attributed to medication cessation.

In addition, a retrospective examination will be performed to assess improvement in the control group before / after intervention as a measurement of contamination. We expect that providers who receive AKI alerts on some patients may be more likely to look for AKI in other patients, potentially diluting the effect of the intervention – this pre/post intervention analysis will help in assessing that level of contamination.

Because we are enrolling patients across four sites, we will do an exploratory analysis to determine the efficacy of alerts independently at each hospital.

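### The exploratory by-hospital analysis includes no test of whether the alert effect differs between hospitals, so it cannot answer the question the prior trial raised.

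*Combined protocol and SAP*

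**What the plan says.** Section I, item 3 (Background) reports that the prior alert trial was null overall but that "there was substantial heterogeneity among the study sites", with signals of harm at its two non-teaching hospitals. Section I, item 10 (Risks) acts on this: "Because of this, we will no longer be enrolling in the non-teaching hospitals for this study".

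Section I, item 13 (Statistical Considerations) sets the primary analysis as a single chi-square test with CMH stratification over the four remaining hospitals. It then adds: "we will do an exploratory analysis to determine the efficacy of alerts independently at each hospital". That sentence is all the plan says about differences between hospitals. It names no homogeneity test, no arm-by-hospital term, no threshold and no form of reporting. The only interaction term in the section is intervention by time of year.

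The planned hospital sizes are 2447 (Yale New Haven), 1214 (St. Raphael's), 910 (Bridgeport) and 489 (Greenwich), which sum to 5060.

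**The concern.** The CMH test is aimed at an effect common to all hospitals. Whether the effect is in fact common is a different question, and the sponsor's own history makes it a live one: differences between hospitals in the prior trial have already changed where this trial enrolls. The one analysis that touches the question looks at each hospital alone. Hospital sizes differ fivefold (2447/489 = 5.0), so a comparison of four separate results mostly reflects which hospitals are large enough to detect the effect.

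Two misreadings are possible. Chance differences between small hospitals could be taken as real, and a real difference could pass without ever being tested. Either could influence where alerts are kept, dropped or studied next.

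**Working it through.** **Inputs from item 13.** Control rate: "Our preliminary data suggests that 18.2% of patients would experience the primary outcome of progression of AKI, dialysis, or mortality". Design effect: "We determined that a relative 20% reduction to 14.6% would be clinically significant". Method: "a two-sided Cochran-Mantel-Haenszel (CMH) method will be used for the sample size calculation". Level: "The alpha significance level of the test was set at 0.05". Size: "A total sample size of 4600 patients (i.e., 2301 per group) achieves at least 90% power to detect this degree of change". Hospital sizes are as listed above, with equal allocation.

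**Assumption.** Each hospital is read at two-sided p<0.05. The documents state no such rule.

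**Step 1: reproduce the plan's figure.** With p1 = 0.182, p2 = 0.146 and mean rate 0.164, n per arm for 90% power is

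[1.96·√(2·0.164·0.836) + 1.2816·√(0.182·0.818 + 0.146·0.854)]² / 0.036² ≈ 2222,

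or 4444 in total for a fixed design. Power at 2300 per arm is 0.910. A group sequential design with the stated spending functions and one look at 50% raises the total to about 4670. The stated 4600 at 90% power or more is therefore reproduced closely enough to use these inputs.

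**Step 2: power at each hospital for the same effect.** With n = N/2 per arm, SE0 = √(2·0.164·0.836/n) and SE1 = √((0.182·0.818 + 0.146·0.854)/n), power is Φ[(0.036 − 1.96·SE0)/SE1]. The chance of a point estimate on the harm side is Φ(−0.036/SE1).

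| Hospital | N | SE0 | SE1 | Power | Harm-side estimate |
|---|---|---|---|---|---|
| Yale New Haven | 2447 | 0.01497 | 0.01495 | 0.672 | 0.008 |
| St. Raphael's | 1214 | 0.02125 | 0.02123 | 0.395 | 0.045 |
| Bridgeport | 910 | 0.02455 | 0.02452 | 0.311 | 0.071 |
| Greenwich | 489 | 0.03349 | 0.03345 | 0.188 | 0.141 |

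**Step 3: combine the four hospitals.**
- All four significant: 0.672 × 0.395 × 0.311 × 0.188 = 0.015.
- None significant: 0.328 × 0.605 × 0.689 × 0.812 = 0.111.
- Mixed: 1 − 0.015 − 0.111 = 0.873 (0.873 also in a 200,000-run simulation with simple randomization).
- At least one harm-side estimate: 1 − 0.992 × 0.955 × 0.929 × 0.859 = 0.244.

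**Step 4: sensitivity of the mixed share.**
- Common risk ratio at a control rate of 18.2%: 91% at 0.75, 70% at 0.85, 44% at 0.90. With no effect, 1 − 0.95⁴ = 18.5% for at least one significant hospital.
- Hospital sizes scaled to the 4592 total given in Section III: 85%.
- Prior-subset rates by hospital from item 11 with a risk ratio of 0.8: 88% using control-arm rates, 90% using both arms pooled.

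**Step 5: what a homogeneity test would do.** In the Step 3 simulation, with identical effects, a 3-df test (Cochran's Q on log odds ratios) rejects in 4.7% of trials, so it holds the false-difference rate near 5%. Its power is modest. With a risk ratio of 0.8 at three hospitals, it rejects in about 12% of trials if Greenwich has 1.0 and about 45% if Greenwich has 1.25.

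**Step 6: the protocol's own tables.** From the item 11 counts, alert/control risk ratios for the primary outcome are 1.22 (95% CI 0.95–1.56) at Yale New Haven, 1.06 (0.71–1.59) at St. Raphael's, 0.74 (0.48–1.14) at Bridgeport and 1.53 (0.86–2.72) at Greenwich. The Breslow-Day statistic over these four is 5.31 on 3 df, p = 0.15. That is inconclusive, but the four separate p-values printed there do not address the question at all.

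**The case against.** The strongest defense is that nothing in the plan depends on this analysis. It is labelled exploratory, the efficacy conclusion rests on the pooled CMH test, and the stopping and final thresholds attach to the primary outcome. That stands. A reader might infer that the plan judges efficacy hospital by hospital; the text does not support this.

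The 87% also needs its limits stated. It depends on a p<0.05 reading that the plan does not prescribe; the results could equally be shown as four estimates with intervals. It applies at the design effect, not to any identical effect. And mixed means significant at some hospitals and not at others, which is ordinary low subgroup power. A reader might take it to mean opposite findings, but significant benefit at one hospital with significant harm at another occurs in only about 0.16% of simulated trials.

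The prior trial tested a different alert in a broader population, and the hospitals with harm signals were removed as a safety precaution. Heterogeneity there is a reason to examine hospitals here, not evidence that they differ here.

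Finally, the homogeneity test is weak with four hospitals (Step 5), so it should not be the sole arbiter. This limits what the remedy can deliver. It does not make separate p-values a better answer, because they do not estimate the difference between hospitals.

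**Conclusion.** The gap is real and modest. The exploratory by-hospital analysis has no test of homogeneity, although the sponsor reports heterogeneity between hospitals in its own prior trial and changed its sites because of hospital-level results. If each hospital is read at two-sided p<0.05, an identical 18.2% versus 14.6% effect gives mixed significance about 87% of the time at the planned sizes (about 70% at a risk ratio of 0.85 and 44% at 0.90). At least one harm-side point estimate appears about 24% of the time at the design effect. Separate analyses therefore cannot show whether hospitals differ.

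The primary pooled conclusion, sample size and conduct are unaffected. A reader might also infer that harm at a single hospital should never be read by itself. The documents do not support that: items 11 and 12 suspend enrollment on a harm signal, and that safety review must not be overridden by an efficacy-reporting rule.

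**What to change.** In Section I, item 13, keep the by-hospital analysis exploratory and replace the sentence on separate efficacy with three commitments:

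1. Report a Breslow-Day test, or an arm-by-hospital interaction in a logistic model, beside the CMH result.
2. Show hospital-specific risk ratios with 95% confidence intervals, and the pooled estimate, in one display. Partially pooled hospital estimates are optional.
3. Base any statement that the effect differs between hospitals on the interaction test read together with the intervals, not on separate hospital p-values. State that this does not restrict the safety review in items 11 and 12.

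The cost is a few lines of wording and one extra model on data already collected. The downside is limited power with four hospitals, so a non-significant homogeneity test must not be reported as proof that the effect is the same everywhere.

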lisinopril (PRINIVIL,ZESTRIL) tablet 2.5 mg	Daily		07/01/20	0900
pantoprazole (PROTONIX) 40 mg in sodium chloride 0.9% PF 10 mL (4 mg/mL)	Every 12 Hours Scheduled		06/26/20	2100

PPI - These medications have been linked to acute kidney injury and chronic kidney disease. (1h ago, onward)

This patient is part of a randomized trial. This alert does not fire for all patients with AKI and may not display all relevant medications. Please review all medications on your patient's list for potential discontinuation or dose adjustment. For more information click here: www.akistudy.org/elaia2. For AKI best practices, click here: www.akistudy.org/aki-best-practices.

To review and assess patient medications, click below to enter the medication order entry screen.

CLICK HERE TO OPEN MEDICATION ORDER ENTRY

Acknowledge Reason

I will review the medications Medication clinically indicated Wrong provider

Accept Dismiss

This alert will be received by physicians, physician assistants (PA's), nurse practitioners (NPs), advanced practice registered nurses (APRNs), fellows, and residents who open the order entry screen in the medical record of a patient randomized to the alert arm of the trial, regardless of their relationship with the patient.

The provider will have the option to "dismiss" the alert. However, if dismissed, the alert will continue to pop up for the provider on each subsequent opening of the patient's chart. The alert will only stop firing for any given provider under the following conditions:

- The active nephrotoxin order is discontinued
- The provider acknowledges the alert by clicking "Accept". In this case, the alert will be suppressed for this provider only and for 48 hours.
- The most recent creatinine does not meet AKI criteria
- The patient receives an order for hemodialysis, continuous renal replacement therapy, or peritoneal dialysis
- The patient is transferred to hospice service
- The patient is discharged from the hospital
- The patient expires

Study Outcomes:

Our primary outcome will be a composite of AKI progression, dialysis (hemodialysis, continuous renal replacement therapy, or peritoneal dialysis), or mortality within 14 days of randomization.

Our main secondary outcome will look at the cessation of any of the targeted medications within 24 hours of AKI onset. For individuals with active orders for more than one targeted medication, cessation of any will be adequate to meet this endpoint.

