Other secondary study endpoints will look at a variety of patient outcomes as well as best practice metrics, including the following:

- Inpatient mortality
- Inpatient dialysis
- Discharged on dialysis
- Percent who progress to stage 2 AKI
- Percent who progress to stage 3 AKI
- AKI duration
- 30-day readmission rate
- Cost of index hospitalization
- “Best practice” outcomes: Proportion achieved per patient during index hospitalization:
 - Contrast administration
 - Fluid administration
 - Aminoglycoside administration
 - NSAID administration/cessation
 - ACEi administration/cessation
 - Urinalysis order
 - Documentation of AKI
 - Monitoring of creatinine
 - Monitoring of urine output
 - Renal consults

All investigators will be blinded to the treatment assignment until the end of the trial period.

Clinician Outreach:

While the unit of randomization is the patient, clinicians are considered subjects of this research. We will engage in pre-trial and periodic outreach to all clinicians who may be exposed to this study, informing them of the nature of the study, the fact that it is a randomized trial, and that alerts do not fire for all patients with AKI. We will additionally inform them that limited data is being collected regarding provider behavior. However, we will also make it clear that data subject to clinician behavior (continuation or discontinuation of any medication) will NOT be linked to individual clinicians. All such data will only be analyzed in aggregate. This outreach will be performed through short presentations at divisional conferences and meetings and through regular visits to hospital floors to engage directly with providers. A study Information Sheet will also be handed out to clinicians.

Study Timeline:

We plan to activate our medication-targeted alert in a step-wise fashion throughout our 4 study hospitals. Staggered enrollment will allow for proper pre-trial education as well as adequate site visits, study monitoring, quality control and clinician engagement at each site as roll out begins.

5. Genetic Testing N/A

A. Describe

- i. the types of future research to be conducted using the materials, specifying if immortalization of cell lines, whole exome or genome sequencing, genome wide association studies, or animal studies are planned *Write here*
- ii. the plan for the collection of material or the conditions under which material will be received *Write here*

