- iii. the types of information about the donor/individual contributors that will be entered into a database *Write here*
- iv. the methods to uphold confidentiality *Write here*

B. What are the conditions or procedures for sharing of materials and/or distributing for future research projects? *Write here*

C. Is widespread sharing of materials planned? *Write here*

D. When and under what conditions will materials be stripped of all identifiers? *Write here*

E. Can donor-subjects withdraw their materials at any time, and/or withdraw the identifiers that connect them to their materials? *Write here*

- i. How will requests to withdraw materials be handled (e.g., material no longer identified: that is, anonymized) or material destroyed? *Write here*

F. Describe the provisions for protection of participant privacy *Write here*

G. Describe the methods for the security of storage and sharing of materials *Write here*

6. Subject Population: Provide a detailed description of the types of human subjects who will be recruited into this study.

This study will enroll any hospitalized adult patient currently admitted to any of the four teaching hospitals within the Yale New Haven Hospital system, who has developed incident AKI, and who has also received a nephrotoxic medication within the 24 hours prior to AKI onset. The following are the study's inclusion and exclusion criteria for enrolling subjects.

Inclusion Criteria

1. Adults ≥18 years admitted to a teaching hospital within the Yale New Haven Hospital system (Yale New Haven Hospital, St. Raphael's, Bridgeport Hospital, Greenwich Hospital)
2. Incident Acute kidney injury as defined by Kidney Disease: Improving Global Outcomes (KDIGO) creatinine criteria:
 - 0.3 mg/dL increase in serum creatinine over 52 hours OR
 - 50% relative increase in serum creatinine over 172 hours
3. Received at least one dose of a pre-specified NSAID, RAAS, or PPI agent within 24 hours prior to AKI onset

Exclusion Criteria

1. Dialysis order prior to AKI onset
2. Initial creatinine ≥ 4.0mg/dL
3. Prior admission in which patient was randomized
4. Admission to hospice service or comfort measures only order

5. ESKD diagnosis code
6. Kidney transplant within six months

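### The best-practice outcomes are counted over the whole index stay, including time before randomization, and leave out PPIs and all RAAS agents except ACE inhibitors

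*Combined protocol and SAP*

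**What the plan says.** Section 4 (Study Outcomes) ranks three levels of endpoint. The primary is the 14-day composite. Next comes drug cessation: "Our main secondary outcome will look at the cessation of any of the targeted medications within 24 hours of AKI onset". Below that is a group of other secondary endpoints, which ends with ten best-practice items under the label "Proportion achieved per patient during index hospitalization".

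Two of the ten items concern targeted drugs: "NSAID administration/cessation" and "ACEi administration/cessation". Two others are exposures that the alert does not target by class: "Contrast administration" and "Aminoglycoside administration". The remaining six cover fluids, urinalysis, AKI documentation, creatinine and urine-output monitoring, and renal consultation. No PPI item appears, and ARBs and renin agents are not named.

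Section 6 makes earlier exposure an entry condition: "Received at least one dose of a pre-specified NSAID, RAAS, or PPI agent within 24 hours prior to AKI onset". Section 13 adds an exploratory analysis to "assess whether discontinuation rates differ by medication" and lists the three drug categories as subgroups to be analysed separately.

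**The concern.** These items are meant to show what clinicians did differently because of the alert. Two features weaken them.

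- **Window.** Anything done between admission and randomization cannot have been caused by the alert, yet it counts. It adds the same background to both arms and shrinks the contrast between them.
- **Drug list.** The list does not follow the alert. One of the three targeted classes is missing, and a second is represented by one of its drug groups.

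Process measures matter in this programme. Section 3 reports that the sponsor's previous alert trial found no change in provider actions overall, and signals of harm at two hospitals where process measures were also unchanged. If the new trial gives a puzzling clinical result, these measures are where an explanation would be sought. They also cover behaviour later in the stay. Under section 4 the alert keeps firing after dismissal, and acceptance suppresses it for that provider only, for 48 hours. Its influence can therefore run past the 24-hour window of the main secondary outcome.

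**Working it through.** The plan states no sample size, power or effect size for these outcomes, so there is no figure to reproduce. The check has two parts.

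**1. Window.** Take an item scored as whether an event ever happened during the stay. Let *f* be the share of patients in whom it had already happened before randomization, which randomization makes equal in expectation across arms. Let *p* be the chance of the event after randomization among the rest.

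- Whole-stay proportion in an arm: *f* + (1 − *f*)·*p*
- Difference between arms: (1 − *f*)·(*p*_alert − *p*_control)

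The effect shrinks by the factor (1 − *f*). The documents give no *f* for contrast, fluids or urinalysis, so the dilution on those items cannot be sized. For one group the entry criterion fixes it. In patients who qualified through an NSAID or an ACE inhibitor, with the qualifying dose recorded in the same stay, *f* = 1 for administration of that drug. The administration part of the item then cannot differ between arms; the cessation part still can.

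**2. Drug list.** Inputs from section 3, the sponsor's retrospective data from three hospitals:

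| Class | Exposed at AKI onset, per 100 AKI patients | Continued in next 24 h | Continued exposures per 100 |
|---|---|---|---|
| NSAID | 4.2 | 59% | 4.2 × 0.59 = 2.5 |
| RAAS | 18 | 66% | 18 × 0.66 = 11.9 |
| PPI | 39 | 92% | 39 × 0.92 = 35.9 |
| Sum | 61.2 | | 50.2 |

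- PPI share of summed class exposures: 39/61.2 = 63.7%.
- PPI share of continued exposures: 35.9/50.2 = 71%.

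These are shares of exposures, not of patients, because class overlap is not given. The share of exposed patients who were on a PPI alone can be bounded:

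- Lowest: NSAID and RAAS users are disjoint (4.2 + 18 = 22.2) and all also take a PPI. PPI alone = (39 − 22.2)/39 = 43%.
- Highest: all NSAID users also take a RAAS agent (18 in total) and none takes a PPI. PPI alone = 39/(39 + 18) = 68%.

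So for 43% to 68% of exposed patients the list has no item for the drug that would bring them into the trial. ARB or renin-agent users are in the same position if the ACE-inhibitor item is read literally; the split within the RAAS class is not given.

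**The case against.** The strongest reply is that the provider-behaviour question does not rest on this list. The main secondary outcome counts cessation of any targeted drug, PPIs included, and is anchored to AKI onset rather than admission. Section 13 compares discontinuation by class and analyses each drug category separately. This stands, and it limits the point to lower-tier measures. It does not remove it: the main secondary outcome stops at 24 hours, and the by-class comparison is exploratory with no stated window.

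Three stronger readings are tempting, and the documents do not support them.

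- *The list cannot register the actions the alert prompts.* It names NSAID and ACE-inhibitor cessation, so it can register part of them.
- *The whole-stay window biases the comparison.* Randomization balances earlier events in expectation, so the result is dilution, not bias. A patient on a PPI alone also has no listed item fixed by the entry criterion.
- *A working alert could lower the result, because contrast and aminoglycoside use appear among things achieved.* That requires giving a nephrotoxin to count as good practice. Section 3 describes guidelines as favouring avoidance of such exposures, and an analyst would score these items accordingly. The unstated direction is missing detail, not a reversal.

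It is also fair to say that the text allows item-by-item reporting as well as a composite, that the endpoint list is introduced in non-exhaustive terms, and that class labels are loose throughout, so the ACE-inhibitor label may be shorthand. None of this supplies a start at randomization or a PPI item.

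**Conclusion.** The point holds as a limited, easily corrected weakness. As written, the best-practice outcomes count care given before randomization and omit the largest targeted class: about 64% of summed exposures and 71% of exposures continued after AKI in the sponsor's own data.

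The consequence is loss of sensitivity in lower-tier process measures over the rest of the stay. The primary outcome, the main secondary outcome and early PPI cessation are unaffected.

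The sizes rest on retrospective rates from three of the four trial hospitals, on recent exposure there approximating the 24-hour entry window, and on unknown class overlap. A 92% continuation rate shows how often PPIs were continued, not how many would be stopped in response to an alert. The amount of dilution from the window cannot be calculated from the documents.

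**What to change.** Revise the best-practice outcomes before unblinding:

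- Count each item from randomization to discharge.
- Replace the ACE-inhibitor item with the full pre-specified RAAS list, and add a matching PPI administration and cessation item.
- Report each item by arm, whether or not a per-patient proportion is also shown.
- Present contrast and aminoglycosides as exposures, where lower is better, rather than as items achieved.

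The cost is outcome wording and queries of the same electronic record. The downside is that the outcome will no longer be identical to the listed one, so the change should be dated and documented.
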